4.8 Storage of randomization codes

See also section 4.3.1

The Principal Investigator will be provided an envelope with information for decoding the group of patient by randomization ID. The Principal Investigator will be responsible for storage of envelope with decoding information so as to provide confidentiality and integrity of information, but with preserved possibility of access, if it is necessary to disclose randomization ID. Upon completion of the study, the Principal Investigator must return the envelope to the Sponsor despite the fact whether it was opened or not.

In case of unintentional unblinding of female patient or staff of the clinical site, the Sponsor should be informed immediately.

In cases when unblinding of the treatment group and the drug administered is required to provide safety of the study subject (for example, in case of AR development), unblinding should be

performed after approval and consent of the Sponsor's medical expert. If it is technically impossible, and unblinding is required by vital indications, the medical expert of the Sponsor should be informed on the given fact as soon as possible.

Unblinding of randomization ID, in general, will be performed upon completion of the study and database shutdown.

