4.3 Measures aimed at minimization of subjectivity

4.3.1 Randomization procedure

After signing informed consent for participation in the present study by female patient, confirmation of inclusion criteria presence and non-inclusion criteria absence, all the study subjects will be distributed into groups of treatment by method of centralized block randomization in 1:1:1:1 ratio, without stratification by center using online IWRS system (Interactive Web Response System). Randomization ID of patient will be assigned to a female patient as per the order of access to IWRS system. Whereby randomization IDs corresponding to administration of the test drug or the placebo will be randomly assigned to the equal number of patients.

1. Placebo group, 1.5 mL/kg – up to 30 screened female patients which corresponds to 26 randomizations and 24 completed cases
2. Placebo group, 2.4 mL/kg – up to 30 screened female patients which corresponds to 26 randomizations and 24 completed cases
3. Seroguard group, 1.5 mL/kg – up to 30 screened female patients which corresponds to 26 randomizations and 24 completed cases
4. Seroguard group, 2.4 mL/kg – up to 30 screened female patients which corresponds to 26 randomizations and 24 completed cases

A block generation of randomization sequence will be used for generation of randomization list. Randomization list will be generated in statistics software using random number generator at the stage of preparation for the study

Only randomization ID of the study female patient will be recorded in CRF without specifying the drug administered.

The Investigators will pass an online training on using IWRS system.

Register of screened and randomized female patients will be performed for all the sites. Form of register is provided in the Study Site File. Completion of the form should be performed by the Investigator on a regular basis with entering all the required data.

4.4 Description of the drugs used in the study – description of the dosage form, packing and labeling

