Completion of main documentation of the clinical study – primary medical documentation and CRF – is obligatory for all the subjects of the study.

The Investigator is responsible for complete and precise completion of CRF. All the data recorded in CRF should be reflected in the primary medical documentation of the study subject in print format or in written records made by the Investigator or other authorized person of the clinical site.

All planned data on participation of a female patient in the study are recorded in CRF according to the primary documentation. CRF should also contain data on completed participation by female

patient in the study. CRF should be completed within 5 days after visit of the study subject in the clinical site. CRF should be completed in a legible handwriting with black ink. The mistakes made in the text should not be corrected over the record or erased slightly, or deleted using correction fluid. Instead of this, an error is crossed out with a straight line, a corrected text or digit is written above it as well as signature, date and initials of the Investigator. For all the omitted data, explanations in CRF should be provided, which will be realized by presence of a special tag field (“tick”), confirming omission of data. If required, on the page of comments in CRF with reference to respective page, explanations of data omission reasons will be provided. CRFs should be signed by Co-Investigator and Principal Investigator. The signatures confirm that the information contained in the CRF is true.

All the information on the study and the collected data are strictly confidential. The Investigator has a right to report information on the study to persons not directly participating in the study performance, only after permission of the Sponsor.

A final report consisting of statistical and clinical report is prepared after database shutdown and completion of statistical handling of the study results.

The final report is signed by the Principal Investigator of the clinical site, who confirms the results and inferences of the study by affixing a seal of his (her) institution.

14 Finance and insurance

Finance of the present study is performed by the Sponsor company through CRO. Before the study beginning, respective agreement will be concluded between CRO and each study site.

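### As worded, section 4.8 provides one decoding envelope for a central list, so an emergency opening for one woman could unblind others at the site; a code break should reveal one subject only

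*Protocol*

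**What the plan says.** Section 4.8 (Storage of randomization codes) states that "The Principal Investigator will be provided an envelope with information for decoding the group of patient by randomization ID". The envelope stays singular throughout: the holder keeps it confidential, intact and accessible, and at the end of the study "the Principal Investigator must return the envelope to the Sponsor despite the fact whether it was opened or not". Unblinding for a subject's safety is to be "performed after approval and consent of the Sponsor's medical expert". If that is technically impossible and the indication is vital, the expert is informed as soon as possible. Accidental unblinding must be reported to the sponsor at once.

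Section 4.3.1 (Randomization procedure) sets the allocation as a "method of centralized block randomization in 1:1:1:1 ratio, without stratification by center using online IWRS system". It adds that "Randomization ID of patient will be assigned to a female patient as per the order of access to IWRS system" and that "Randomization list will be generated in statistics software using random number generator at the stage of preparation for the study". The CRF carries the randomization ID without the drug.

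Section 9.2 plans at least 104 randomized women, 26 in each of four groups. Section 13 indicates that the Principal Investigator is a site role: "The final report is signed by the Principal Investigator of the clinical site".

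**The concern.** An emergency code break should reveal what is needed for one patient and nothing more. With a single envelope serving a central list that is not divided by site, opening it properly for one woman would put the codes of others in front of site staff. Because the ID is recorded in the CRF, anyone who has seen the list can read off the group of any woman at that site, including a later one as soon as her ID is issued.

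The outcomes exposed are those judged at the site. Investigators assess the causality of adverse reactions and the clinical significance of laboratory and ECG findings (sections 4.2.3.5, 4.2.3.6, 8.2 and 8.3). Five of the six secondary efficacy endpoints in section 4.1, all but the change in adhesion thickness on MRI, rest on transvaginal ultrasound. Section 4.2.3.6 requires the ultrasound to be video-recorded and the disc kept with the primary documentation, but describes central reading only for MRI.

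**Working it through.** **Length of the list.** The synopsis inputs are p1 = 0.45, p0 = 0.10, margin 0.05, one-sided α = 0.05 and power 80%. With the usual variance term, n = (0.45 × 0.55 + 0.10 × 0.90) × ((1.645 + 0.842)/0.30)² = 23.18, so 24 per group, as stated. Adding 10% gives 24 × 1.10 = 26.4, stated as 26. Then 4 × 26 = 104, which agrees with section 9.2. (The variance term printed in the protocol and the 5% placebo rate in the symbol list of section 9.2 would give other sizes. That is a separate matter and does not affect this point.)

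**What one envelope has to contain.**
1. The list is generated before the study (section 4.3.1).
2. IDs are issued in order of IWRS access across all sites, and the list is "without stratification by center using online IWRS system" (section 4.3.1).
3. So no site can know in advance which IDs its women will receive.
4. Section 4.8 describes one envelope that decodes group from ID.
5. If it was prepared in advance and must decode any woman at the site, it must cover IDs well beyond hers, up to the full 104.

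**Codes revealed by one opening after k women have been randomized, on a list of 104.**

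| k | Codes revealed | Of these, not yet issued (104 − k) |
|---|---|---|
| 20 | 104 | 84 |
| 26 | 104 | 78 |
| 52 | 104 | 52 |
| 78 | 104 | 26 |

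If k is equally likely to be any value from 1 to 104, the average number not yet issued is 51.5. A break limited to one subject reveals 1 code, and none that is unissued.

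**What those counts mean.** They are codes visible, not women whose assessments are biased. Staff at the site assess only their own patients. Women who have finished Visit 3 have no scheduled assessment left to influence. The assessments at risk are those of women at that site still in follow-up when the envelope is opened, and of every woman randomized there later. The protocol text does not give the number of sites, so this number cannot be computed; it lies below 103 (104 less the woman concerned).

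**Concealment before randomization.** An unissued code predicts the next allocation only if the site knows which ID comes next. That depends on how many women all sites have randomized, so prediction is partial. Once an ID is issued, the group of that woman is fully known.

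**The case against.** The best reply is that section 4.8 never itemises the envelope's contents or says when it is supplied. The text is a translation, the patient and the ID are also in the singular, and a per-patient envelope is a possible reading. Section 4.3.2 (Blinding procedure) appears in the contents list but its text was not available, and code-break detail may stand there. The number of holders is also inferred: section 13 points to a site role, while section 9.5 has Investigators reporting to the Principal Investigator, and the form in section 17.1 combines the role with that of coordinator. These points stand as limits on certainty. They do not remove the problem, because the literal wording describes one envelope and nothing in the available text restricts an opening to one subject. A single trial-wide holder would still expose the whole list.

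The safeguards are real. Approval by the sponsor's medical expert, secure storage and return of the envelope make openings rarer and traceable. The drug is given once, at surgery, so there may be few occasions to break a code; the protocol gives no expected frequency. But none of these measures limits what an opening reveals.

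Three stronger readings are tempting, and the protocol does not support them:
- **Allocation concealment at the site would end.** It would be only partly lost, because the next ID depends on accrual at other sites.
- **The primary endpoint would be compromised.** Section 4.2.3.6 sends the MRI records for central evaluation in an independent laboratory with the therapy group blinded. A reader might add that randomization precedes surgery, so knowledge of the group could influence surgical decisions. Nothing in the protocol shows this or allows it to be sized, and the point does not rest on it.
- **The existing IWRS can already break a single code.** The protocol describes the IWRS only for randomization and ID assignment.

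**Conclusion.** The point holds as a weakness in a stated procedure. Read literally, sections 4.8 and 4.3.1 together mean that one justified opening could reveal up to the whole list, at least 104 codes, where 1 is needed. It could unblind the site to its other patients and, as their IDs are issued, to its later ones. The consequence is possible bias in site-judged adverse reaction causality and clinical significance and in the five ultrasound secondary endpoints.

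This rests on three assumptions: that there is one envelope per holder, that it was prepared in advance to decode any woman at the site, and that section 4.3.2 does not already restrict a break to one subject. If per-patient envelopes were intended, the exposure disappears and section 4.8 needs only to say so. The figure of 104 is a ceiling on codes revealed at one opening, not an estimate of women affected. This is an inexpensive improvement worth making, not a flaw that undermines the primary analysis.

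**What to change.** Reword section 4.8 so that any code break reveals the allocation of one subject only. Either of two routes would do:
- one sealed, opaque envelope per randomization ID; or
- a per-subject code break in the IWRS, logged with user, time and reason, once it is confirmed that the system supports this or can be configured for it.

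Keep the existing approval by the sponsor's medical expert and the reporting of accidental unblinding. State who holds the code-break material, and align the wording with section 4.3.2.

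The cost is one paragraph of protocol text plus the preparation of individual envelopes or some IWRS configuration. The envelope route does not depend on what the IWRS can do.

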4.9 List of data recorded directly in the CRF and considered as primary

All the data will be initially entered into primary documentation (medical history or medical record) of female patient, and only then they will be transferred into CRF of the study patient.

5 Selection and exclusion of the study subjects

5.1 Inclusion criteria

1. Female patients aged from 18 to 45 years with confirmed diagnosis of pelvic adhesions with indications for surgery (laparoscopic adhesiolysis)
2. Voluntarily and personally signed and dated Form of Informed Consent to participate in the study
3. Female patients with pelvic adhesions confirmed by gynecological examination and USI

5.2 Non-inclusion criteria

1. Female patients having contraindications to operative treatment (including acute or exacerbated chronic adnexal inflammatory process)
2. Body mass index 30.0 kg/m^2 and more
3. Known hypersensitivity to components of the test drug (Seroguard)
4. Pregnancy, lactation or planning for pregnancy during the clinical study
5. Refusal to use effective contraception methods throughout the study
6. Positive HIV, RW, HBV or HCV test results.
7. Alcohol abuse, drug addiction, and toxicomania (except for smoking)
8. Category III and higher by physical status classification of the American Society of Anesthesiologists (ASA).
9. Purulent process in the abdominal cavity
10. Disseminated endometriosis
11. Elevated WBC count in complete blood count exceeding $10 \times 10^9/\text{L}$

12. Necessity of using any other drugs during the surgery (except for 0.02% chlorhexidine aqueous solution throughout the surgery, as well as the test drug or the placebo (0.9% sodium chloride) in the end of surgery) administered intraperitoneally
13. Concomitant diseases that may require conversion of the surgical intervention by other indications
14. Type I or II diabetes mellitus
15. Deep vein thrombosis and/or PATE at screening or in the history
16. Renal impairment (reduced glomerular filtration rate below 60 mL/min/1.73 m² evaluated by the CKD-EPI equation)
17. Liver disorders determined as more than 2-fold elevation of the upper limit of normal of one of the following enzymes: ALT, AST, GGTP, AP, or more than 2-fold elevation of total bilirubin level
18. Myocardial infarction within 6 months before screening
19. Any concomitant diseases accompanied by heart failure.
20. Clinically significant changes in ECG (in Investigator's opinion).
21. Any concomitant diseases accompanied by respiratory failure
22. Any oncology disease within 3 years before enrollment into the study.
23. Systemic inflammatory diseases.
24. Diseases associated with chronic hemorrhages
25. Blood diseases (anemias of any origin, hemoglobinopathies, inherited and acquired coagulopathies, hemostasis disorders, thrombocytopenias, and thrombocytopathias, any hemoblastoses)
26. Any other disease, that, in the Investigator's opinion, may distort the study results or present an additional threat to well-being of a female patient after administration of the study drug
27. Administration of anticoagulants, antiaggregants (except for acetylsalicylic acid at the dose of less than 325 mg/day) at the moment of inclusion into the study or planning to do so during the study.
28. Administration of drugs with pronounced hemato-, hepato-, or nephrotoxic action, drugs of biological origin
29. Necessity of administration of cytostatics, systemic glucocorticosteroids and other immunosuppressive agents in the period of participation in the study.
30. Participation in another clinical study within 30 days before screening
31. Contraindications for performance of MRI (presence of implants or implanted electronic devices)

32. Impossibility or inability to comply with the requirements of the protocol, including those for physical, psychic or social reasons, in Investigator's opinion

5.3 Withdrawal criteria

1. Withdrawal of informed consent by female patient
2. Female patient's non-compliance with the rules of participation in the study.
3. Pregnancy occurrence.
4. Necessity of conversion during surgical intervention
5. Necessity of surgery during the period between adhesiolysis surgery and Visit 3
6. Other reasons occurring during the study and interfering with the study performance in accordance with the protocol.
7. Necessity of drain tube installation revealed during the surgery

5.3.1 Early withdrawal

Patients willing to terminate their participation in the study (recall of informed consent) are withdrawn from the study. Each female patient has a right to terminate her participation in the study at any time without explaining the reasons.

After randomization and beginning of a clinical phase, the Medical Investigator may prematurely exclude a female patient from the study in case of:

- Female patient's refusal to continue participation in the study.
- Occurrence of reasons/appearance of situations threatening safety of female patient found during the study (for example, hypersensitivity reactions, serious life-threatening adverse reactions related to the drug administration, pregnancy of female patient).
- Development of diseases in a female patient described in non-inclusion criteria, required administration of the drugs not permitted by the protocol.
- Appearance of another reasons during the study interfering with performance of the study according to the protocol.

Detection of reasons of withdrawal from the study in patients included into the study leads to their exclusion from the study at the stage of detection of these reasons. In any case of early termination by female patient/withdrawal of female patient from the study, the Medical Investigator should make a respective record in the CRF with obligatory indication of early termination or withdrawal from the study as well to inform the Sponsor's representative.

5.3.2 Collection of data on the study participants early terminated their participation in the study

All the cases of withdrawal of female patients from the study will be documented. The Investigator should specify date and reason of early withdrawal from the study in the primary documentation and the CRF in section for the study completion.

If a patient terminates participation in the study voluntarily, the Investigator should try to find out the reason. If an early termination of a female patient is related to AR or serious adverse reaction (SAR), the Investigator should make every effort for collection of information on its outcome and to record it in the CRF, section on AR/SAR. If exclusion/withdrawal from the study was related to SAR, it is necessary to follow the procedure on notification of the Sponsor on SAR (see section 8.3).

All ARs developed during the study in female patients withdrawn from the study, including ARs to the moment of terminating participation of female patient in the study will be analyzed and included into a final report on the study performance.

If withdrawal/exclusion from the study was after administration of the study drug to a female patient, her data collected before the moment of withdrawal/exclusion from the study will be analyzed during analysis of safety and, if possible, during analysis of efficacy. Approaches to analysis of data on the study participants early terminated their participation in the study are described in section 9.5.

